Data analysis	
 • The data will be summarized with respect to demographic, baseline characteristics, safety observations and efficacy measurements. Categorical data will be presented as frequencies and percentages. For continuous data, mean, standard deviation, median, minimum, and maximum will be presented. • The primary analysis will be based on the calculation of the observed pyrexia event rate (composite rate of grade 3/4 pyrexia, hospitalization due to pyrexia or permanent treatment discontinuation due to pyrexia) and its 95% two-sided exact confidence interval (Clopper and Pearson 1934) up to 12 months of therapy. • The study will meet its primary objective if the upper bound of the two-sided 95% CI is less than 20%. • The secondary endpoints RFS and OS distribution will be estimated by using Kaplan-Meier approach. • One IA for futility of the primary endpoint and the secondary endpoint RFS is planned for the study when approximately the first 200 subjects dosed have been followed for 6 months (either completed 6 months of treatment or discontinued treatment earlier.) • The sample size of 600 subjects has been chosen so that the study operating characteristics comply with the requirement to have a high probability (> 95%) to declare futility at IA if the true 12-month pyrexia event rate is $\geq 20\%$.
Key words	dabrafenib, trametinib, adjuvant, melanoma, combination treatment, pyrexia

Amendment 2 (12-Mar-2019)

As of 12-Mar-2019, 86 sites have been initiated, 311 subjects have enrolled into the study, and 234 subjects have started treatment in the study.

Amendment rationale

The primary purpose of this protocol amendment is to implement clinically relevant feedback received from the Health Authorities and participating center's Ethics Committees upon review of the protocol. In addition, study population inclusion criteria was expanded, clarifications and corrections are made throughout the protocol, as well as editorial change to improve flow and consistency.

Changes to the protocol

Changes to specific sections of the protocol are shown in the track changes version of the protocol using strike through red font for deletions and red underline for insertions

- Protocol Summary Section updated to match the body of the protocol
- List of Abbreviations was updated
- Section 3 - Study Design: Treatment Period was clarified:
 - One study month is equal to 4 weeks or 28 days.
- Section 5.1 - Inclusion Criteria

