12.7 Interim analyses

One IA for futility of the primary endpoint is planned for the study when approximately the first 200 subjects dosed have been followed for 6 months (either completed 6 months of treatment or discontinued treatment earlier.) At the time of this IA, the futility of a secondary efficacy endpoint RFS will also be assessed. This analysis will allow assessing the impact of the adapted pyrexia AE-management algorithm on both the pyrexia event rate and the RFS rate at 6 months. The DMC will review the IA results and make a recommendation using the scenarios provided below. Any decision to stop or continue the pyrexia management algorithm will be made based on all data available at the IA cut-off taking the futility analysis into account.

From the COMBI-AD study that used the approved pyrexia management algorithm, the pyrexia event rate (composite rate of grade 3/4 pyrexia, hospitalization due to pyrexia, or permanent treatment discontinuation due to pyrexia) at 12 month observed for dabrafenib + trametinib (N=435) was: 20% with 95% CI (16%, 24%). Under the new pyrexia treatment algorithm, an observed primary endpoint rate of at least 20% may indicate lack of improvement of the new algorithm. Assessment of futility for primary endpoint will be based on the calculated Bayesian predictive probabilities of the event that observed pyrexia event rate will be 20% or more in the FAS, if the study is continued beyond the interim (i.e. till the primary analysis).

The pyrexia event rate is assumed to be binary and the number of subjects with pyrexia events is assumed to follow a binomial distribution. Suppose the prior belief regarding the probability of event rate (π) is that it has a beta distribution with parameters a_0 and b_0 . If there are x events out of n subjects, then the posterior distribution for π is beta with parameters $a_1 = a_0 + x$ and $b_1 = b_0 + n - x$. Now let Y represent the number of subjects with pyrexia events from m future observations, then the (posterior) predictive distribution of Y conditional on the observed data at the interim (x events out of n subjects) is a beta-binomial distribution described by

$$p(Y = y|x, n) = \binom{m}{y} \frac{B(a_0+x+y, b_0+n-x+m-y)}{B(a_0+x, b_0+n-x)}$$

where $B(a, b)$ is the beta function.

A diffuse (highly non-informative) prior distribution of the composite rate with a skeptical expectation of 20%, namely Beta (0.25, 1) is assumed.

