Under these assumptions, the DMC will be provided the predictive probability of observing pyrexia event rate of $\geq 20\%$, a criterion that may trigger consideration for stopping the study taking account of all available data and not just the pyrexia event rate data required for determination of futility.

Table 12-3 shows the predictive probabilities of observing pyrexia event rate $\geq 20\%$ ($n=200$) under different interim results. For illustration, with 200 subjects at IA, if the observed pyrexia event rate is 22%, the probability of observing the pyrexia event rate $\geq 20\%$ at primary analysis is $> 80\%$. The DMC might interpret this scenario as an outcome where stopping the study for futility may be a sensible option. If the observed pyrexia event rate is 18% at IA, the probability of observing the pyrexia event rate $\geq 20\%$ at primary analysis is $< 20\%$.

Table 12-3 Predictive probability of observing composite pyrexia event rate greater or equal 20% (n=200) in the safety set at primary analysis (600 subjects) under different interim results

Observed rate at IA (n=200)		Predictive probability of observing pyrexia event rate \geq 20% at primary analysis*
# of subjects with pyrexia events	%	
30	15	0.0135
32	16	0.0392
34	17	0.0943
36	18	0.1913
38	19	0.3318
40	20	0.5000
42	21	0.6673
44	22	0.8058
46	23	0.9015
48	24	0.9569
50	25	0.9838
52	26	0.9948
54	27	0.9986
56	28	0.9997
58	29	0.9999
60	30	1.0000

*prior distribution Beta (0.25, 1) is assumed.

At the time of this IA, the DMC will also be provided with interim results for the secondary endpoint RFS. Similar to the futility analysis for the primary endpoint, Bayesian predictive probabilities of the RFS rate will be provided.

From the COMBI-AD study, the Kaplan-Meier estimated RFS rate at 12 month for control group and treatment group were: 56% with 95% CI (51%, 61%) and 88% with 95% CI (85%, 91%), respectively. We consider the futility threshold of 12-month RFS rate of 61%, which is the upper bound 95% CI of control group, and calculate the predictive probability (PP) as follows:

$$PP = \text{Prob. [Observed 12 month RFS rate} \geq 61\% \mid x, n; x \text{ successes among } n \text{ subjects}]$$

The DMC will be provided the predictive probability of observing RFS of $\geq 61\%$, a criterion that may trigger consideration for stopping the study taking account of all available data and not just the RFS data required for determination of futility.

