12.8 Sample size calculation

The sample size calculation is based on the primary variable. The sample size of 600 has been chosen so that the study operating characteristics comply with the requirement to have a high probability (e.g. > 95%) for futility at IA if the true 12-month pyrexia event rate is > 20%, e.g., when the true pyrexia event rate is 27%, the probability is 95.5% for futility.

Operating characteristics are described below (see [Table 12-5](#)). For illustration, if the true 12-months pyrexia event rate is 30%, then there is a high chance (99.6%) of futility at the time of the IA, and the probability to continue the study and conclude success is lower than 0.001.

If the true pyrexia event rate is 20%, then the probability of observing a pyrexia event rate < 20% (i.e., study success for primary analysis) is 43.4%. If the true pyrexia event rate is lower (for example 18%), then there is 83.9% probability of declaring study success for primary analysis.

Table 12-5 Operating Characteristics

True 6 -month event rate	Probability to stop the study at IA	Probability of success at primary analysis (i.e., not stop at the IA and observe event rate < 20% at primary analysis)
16%	0.016	0.980
17%	0.040	0.939
18%	0.086	0.839
19%	0.161	0.661
20%	0.265	0.434
21%	0.391	0.228
22%	0.528	0.094
25%	0.856	0.001
26%	0.917	<0.001
27%	0.955	<0.001
28%	0.978	<0.001

True 6 -month event rate	Probability to stop the study at IA	Probability of success at primary analysis (i.e., not stop at the IA and observe event rate < 20% at primary analysis)
30%	0.996	<0.001

Probabilities are calculated based on the exact binomial distribution.

13 Ethical considerations and administrative procedures

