## 6 Sample size calculation

As per the protocol amendent version dated 09-May-2019, approximately 600 subjects were planned to be enrolled to receive dabrafenib (150 mg BID) and trametinib (2 mg once daily) combination therapy for 12 months. Due to global drug supply availability, the enrollment of patients was slower than anticipated, resulting in the final sample of 556 enrolled patients in the study by the end of anticipated recruitment period. The final sample size is reasonably close to

the planned target. The impact of the reduced sample size for the interim analyses has been discussed in detail in the Interim SAP (dated 21-Nov-2019) and DMC charter (17-Jan-2020). See Section 2.8 and Appendix B respectively for details.

The sample size calculation was based on the primary variable. The protocol amendment dated provided justification for the planned sample size of 600. However the current sample size of 556 demonstrates that the study operating characteristics comply with the requirement to have a high probability (e.g. > 95%) for futility at IA if the true 12-month pyrexia event rate is > 20%, e.g., when the true pyrexia event rate is 27%, the probability is 95.5% for futility at interim analysis.

Detailed Operating characteristics are described below (see [Table 2-8](#)). For illustration, if the true 12-months pyrexia event rate is 30%, then there is a high chance (99.6%) of futility at the time of the interim, and the probability to continue the study and conclude success is lower than 0.001.

If the true pyrexia event rate is 20%, then the probability of observing a pyrexia event rate < 20% (i.e., study success for primary analysis) is 46.3%. If the true pyrexia event rate is lower (for example 18%), then there is 84.6% probability of declaring study success for primary analysis.

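### The sample size is justified by a >95% chance of futility at the interim for true rates at or above 20%, but the plan's own tables give 26.5% at 20% and pass 95% only at 27%

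*Protocol*

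**What the plan says.** The Data analysis row of the Protocol summary gives the reason for 600 subjects, namely that the design should "comply with the requirement to have a high probability (> 95%) to declare futility at IA if the true 12-month pyrexia event rate is" no lower than 20%. It has no qualifier, example or table.

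Protocol 12.8 sets the requirement for a true 12-month rate above 20%, writes the level as an example (e.g. > 95%), and illustrates it: "when the true pyrexia event rate is 27%, the probability is 95.5% for futility". Table 12-5 follows. Its rows are headed as 6-month event rates, although the text reads them as 12-month rates: "if the true 12-months pyrexia event rate is 30%, then there is a high chance (99.6%) of futility at the time of the IA".

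SAP 6 carries this over to the achieved sample size: "However the current sample size of 556 demonstrates that the study operating characteristics comply with the requirement to have a high probability" of futility for rates above 20%. Table 2-8 has the same 6-month heading and the same stopping column as Table 12-5. SAP 6 also says: "The impact of the reduced sample size for the interim analyses has been discussed in detail in the Interim SAP" and the DMC charter. Neither document is available here.

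Protocol 12.7 makes futility advisory. Any decision "will be made based on all data available at the IA cut-off taking the futility analysis into account". For an observed interim rate of 22%, where the predictive probability of a final rate of at least 20% is above 80%, it says: "The DMC might interpret this scenario as an outcome where stopping the study for futility may be a sensible option". It contrasts this with a second case: "If the observed pyrexia event rate is 18% at IA", that predictive probability is below 20%.

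**The concern.** The sentence is the stated reason for the sample size. A reader would take from it that an algorithm no better than the historical control was almost certain to be flagged at the interim, and might then read the recommendation to continue as strong evidence against a rate of 20% or a little more. The tables do not support that reading.

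SAP 6 goes further and says that 556 demonstrates the property. The stopping column, however, is the same for 600 and 556, so it shows nothing specific to 556.

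**Working it through.** **Check from the printed figures alone.** Stopping at the interim and continuing to success exclude each other, so P(stop) ≤ 1 − P(success).

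| True rate | Success, N=600 (Table 12-5) | Largest possible P(stop) | Success, N=556 (Table 2-8) | Largest possible P(stop) |
|---|---|---|---|---|
| 20% | 0.434 | 0.566 | 0.463 | 0.537 |
| 21% | 0.228 | 0.772 | 0.258 | 0.742 |
| 22% | 0.094 | 0.906 | 0.115 | 0.885 |

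All are below 0.95, whatever cutoff was used.

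**Reproducing the stopping column.** Inputs:
- 200 subjects at the interim (Protocol 12.7).
- Exact binomial distribution (footnote to Table 12-5).
- The 22% illustration, i.e. 44/200. Under the Beta(0.25, 1) prior and N=600, 44 is the first count with predictive probability above 80%: 0.741 at 43 and 0.806 at 44, the latter as in Table 12-3.

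P(stop | p) = P(X ≥ 44), X ~ Bin(200, p):

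| p | 20% | 21% | 22% | 25% | 26% | 27% | 28% | 30% |
|---|---|---|---|---|---|---|---|---|
| Computed | 0.265 | 0.391 | 0.528 | 0.856 | 0.917 | 0.955 | 0.978 | 0.996 |
| Tables 12-5 and 2-8 | 0.265 | 0.391 | 0.528 | 0.856 | 0.917 | 0.955 | 0.978 | 0.996 |

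All 12 printed rows match. Cutoffs of 42, 43 and 45 do not fit. The untabulated rows are 0.658 at 23% and 0.770 at 24%. The probability equals 0.95 at p = 26.8%.

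**The success columns** reproduce as P(X ≤ 43 and final rate < 20%), with the same p for the first 200 subjects and the rest. At 20% this gives 0.434 (N=600) and 0.463 (N=556); at 18%, 0.839 and 0.846. The tables therefore use one true rate at both time points.

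**Actual interim size.** SAP 4 reports 203 subjects. The smallest count giving at least 22% is 45 (45/203 = 22.2%). P(X ≥ 45), X ~ Bin(203, p), is 0.244 at 20%, 0.909 at 26% and 0.951 at 27%.

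**Cutoff needed for the stated property, n=200:**
- At a true 20%, at most 31/200 (15.5%): P(X ≥ 31) = 0.957, P(X ≥ 32) = 0.937.
- At a true 21%, at most 33/200 (16.5%): P(X ≥ 33) = 0.954.

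With x events at the interim and Y ~ BetaBinomial(400, 0.25 + x, 201 − x), the predictive probability P(x + Y ≥ 120) is 0.024 at x = 31 and 0.062 at x = 33. A cutoff of 31 would also stop a study whose true rate is 16% with probability 0.61, against 0.016 in the tables.

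**Six against twelve months.** The share of 12-month events that occur by month 6 is not in the documents. Assuming 80%, 90% or 100%, a true 12-month rate of 20% becomes 16%, 18% or 20% at six months, and P(stop) is 0.016, 0.086 or 0.265. A cumulative rate cannot fall over time, so 0.265 is an upper bound.

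**Role of N.** At a fixed cutoff, P(stop) depends only on the interim sample, so 600 and 556 give identical values. N enters only through the predictive probability, which at 44/200 is 0.806 for N=600 and 0.794 for N=556. If the 80% level were applied for 556, the cutoff would be 45/200 and P(stop) would be 0.211 at 20%, 0.888 at 26% and 0.937 at 27%.

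**The case against.** - **Loose wording.** Protocol 12.8 and SAP 6 write the level as an example, give a correct case at 27%, and print the full table straight afterwards. A careful reader has the right figures at hand. This makes those two places milder than the Protocol summary. It does not make the sentence true: the example marker qualifies the probability level, not the range of rates, and 26.5% to 53% at 20% to 22% is not a high probability on any reading.
- **An unseen rule.** The interim SAP or DMC charter may hold a different cutoff, and Protocol 12.7 fixes no binding one. The 44/200 rule is inferred, although it reproduces every row. But a cutoff that delivered the claim would mean stopping at 15.5% observed, where the predictive probability of failure is 2.4%. That is incompatible with the scheme in Protocol 12.7. The first check above needs no cutoff at all.
- **Low weight.** Futility was advisory, the interim is over, and the success criterion (upper 95% confidence bound below 20%) is stated separately and correctly. No pending decision depends on the sentence. This stands, and it limits the remedy to a note.

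**Conclusion.** The concern holds. The design does not have the property given as the reason for its sample size. At a true rate of 20% the probability of stopping is 0.265 against a stated value above 0.95. The 95% level is reached only at about 26.8%, so 27% is the first tabulated row above it. With the 203 subjects analysed, the figure at 20% is 0.244.

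These figures rest on the illustrative cutoff of 22% observed and on one true rate at the interim and at 12 months. If fewer events have occurred by month 6, the shortfall is larger. The error should be corrected because it is certain and appears in three places. It does not affect the validity of the primary analysis.

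**What to change.** Put one correcting note in the SAP or study report, covering the Protocol summary, Protocol 12.8 and SAP 6:

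1. Replace the claim with, for example: *At the planned interim size, with stopping at an observed rate of at least 22% (44/200, an illustrative, non-binding cutoff) and the same true rate at the 6-month interim and at 12 months, the probability of stopping is 26.5% at a true rate of 20% and exceeds 95% only from about 27%.* Add the values for 45/203: 0.244 at 20% and 0.951 at 27%.
2. Reconcile the 6-month headings of Tables 12-5 and 2-8 with the 12-month text, and state that one rate is used at both time points.
3. Withdraw the statement in SAP 6 that 556 demonstrates compliance. If the interim SAP or DMC charter has a stopping column recomputed for 556, refer to it.

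Optionally, and as a separate matter, show the probability of success under the actual criterion (at most 100/600 or 92/556 events). With the 44/200 stop included as in the tables' own column, and the rates labelled as assumed, it is 0.693/0.662 at 16%, 0.438/0.413 at 17% and 0.213/0.202 at 18%.

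The cost is low. The printed stopping probabilities stay, and there is no new data and no change to the primary analysis. Changing the protocol text would need a written amendment (Protocol 14.1), which this point alone does not warrant.

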1.1 Background

Cutaneous melanoma is the most aggressive form of all skin cancers and has the highest rate of increasing incidence worldwide. The World Health Organization (WHO) estimated that 132,000 melanoma skin cancers occur globally each year (WHO 2017). In the United States (US), it was estimated that there would be 87,110 new cases of melanoma of the skin and an estimated 9,730 people would die of this disease in 2017 (SEER 2017). Surgical excision is the treatment of choice for early cutaneous melanoma and is curative in most cases. However, some patients will subsequently relapse with disseminated disease. High-risk features in the primary tumor (e.g., tumor thickness, ulceration, mitotic rate) and regional lymph node metastasis define patient subsets that are at increased risk for recurrent disease (Balch et al., 2009). Patients with positive Sentinel Lymph Node Biopsy (SLNB) are at higher risk of recurrence, and might be candidates for Complete Lymph Node Dissection (CLND) and/or adjuvant systemic therapy (NCCN V1, 2018). In addition to the recent results with drug therapies, it has been demonstrated by the DeCOG-SLT and the MSLT-2 trials CLND does not improve melanoma-specific survival (Leiter et al., 2016, Faries et al. 2017). It is anticipated that these findings will reduce the number of CLNDs in the management of melanoma (Eggermont et al., 2017).

The overall 5-year relapse-free survival (RFS) rates observed for Stage IIIA, IIIB, and IIIC patients were 63%, 32%, and 11%, respectively. The estimated 5-year survival rates for Stages IIIA, IIIB, and IIIC from the time of the first relapse were 20%, 20%, and 11%, respectively (Romano et al., 2010). According to a multivariate analysis, systemic relapse has been associated with shorter survival than regional relapse, particularly for older patients and patients experiencing a symptomatic relapse. Of note, more than 40% of patients with Stage III melanoma will present with systemic disease at first relapse (observed in 40%, 51%, and 61% of patients with Stage IIIA, IIIB, and IIIC disease, respectively) (Romano et al., 2010).

For patients with completely resected Stage III Melanoma, additional postoperative management options may include high-dose or pegylated IFN, High-dose Ipilimumab, Nivolumab or Dabrafenib/Trametinib for patients with BRAF V600 activating mutation. Selection of active adjuvant treatment in these patients depends on many factors, including patients preference, patient age and comorbidities, and risk of recurrence. (NCCN, V1, 2018)

Prior to the development of checkpoint inhibitor and BRAFV600 targeted therapies, high-dose interferon alfa (IFN α) was the only option for adjuvant treatment of high-risk melanoma that had demonstrated an improvement in overall survival (OS). The use of high-dose IFN α was supported by the results of the Eastern Cooperative Oncology Group (ECOG) 1684 and Intergroup E1694 trials (Kirkwood et al, 1996, Kirkwood et al, 2001, respectively) as well as a meta-analysis that included results from trials with various schedules and doses of IFN α (Kirkwood et al, 2013). Administration of adjuvant high-dose IFN α was associated with numerous serious side effects, including acute constitutional symptoms, chronic fatigue, myelosuppression, hepatotoxicity, and neurologic and psychologic effects, which were experienced to some degree by the majority of patients (Eggermont 2016). IFN α no longer has a well-defined role in the adjuvant setting for cutaneous melanoma. The use of high-dose IFN α for the high-risk node-negative disease may occasionally be an alternative, but its use should be discouraged in favor of clinical trial participation or observation.

Melanoma is a highly immunogenic tumor, initially suggested by observations of spontaneous remissions and identification of lymphocytic responses to primary melanoma (Kirkwood et al.,

2013). With the availability of new therapies (including immune checkpoint inhibitors, agents targeting the BRAF V600 activating mutation and MAPK pathway), significant progress has been made for the treatment of metastatic melanoma, translating into improved progression-free survival (PFS) and OS outcomes (Hodi et al, 2010; Larkin et al, 2015; Larkin et al, 2017; Robert et al, 2015; Long et al, 2015; Robert et al, 2016).

Adjuvant checkpoint inhibitors

Ipilimumab, an immune checkpoint inhibitor targeting CTLA-4, used at a dosage of 10 mg/kg, has shown significant RFS improvement in high-risk Stage III melanoma after complete resection [Hazard Ratio (HR)=0.76, 95% confidence interval (CI): 0.64, 0.89] which later translated into a survival benefit (HR=0.72, 95% CI: 0.58, 0.88) after a median follow-up of 5.3 years (Eggermont et al, 2015; Eggermont et al, 2016). Ipilimumab at a dosage of 10 mg/kg was approved in the adjuvant setting in the US in October 2015. Nivolumab versus ipilimumab have been assessed as adjuvant treatment in resected Stage IIIB, IIIC, or IV melanoma (Weber et al., 2017). The primary endpoint of RFS was met; showing a HR for disease recurrence or death of 0.65 (95 % CI, 0.51 to 0.83; P<0.001) favoring the nivolumab arm. The OS data is not yet mature. Nivolumab at a dosage of 240 mg every 2 weeks in the adjuvant setting was approved in the US in December 2017.

Adjuvant Targeted therapy

In the BRIM8 study, vemurafenib was evaluated as adjuvant treatment in patients with resected BRAF V600 mutant melanoma in two separate cohorts, Stage IIC-IIIB and Stage IIIC. The primary DFS endpoint in the Stage IIIC cohort was not met (HR=0.80; 95% CI 0.54-1.18; p=0.25); the DFS results in the Stage IIC-IIIB cohort showed clinical benefit (HR=0.54; 95%CI 0.37-0.78 p=0.001), although no formal testing was performed. The OS data was not yet mature (Lewis et al., 2017).

The COMBI-AD Study (Study BRF115532, Novartis code: DRB436F2301) evaluated the combination of dabrafenib and trametinib versus two placebos in the adjuvant treatment of advanced melanoma after complete resection. The study enrolled patients with completely resected, histologically confirmed, BRAF V600E/K mutation-positive, high-risk (Stage IIIA, IIIB or IIIC) cutaneous melanoma.

The primary endpoint was RFS, and secondary endpoints included OS, distant metastasis-free survival (DMFS), freedom from relapse (FFR), and safety. The primary endpoint was met, with a 53% decrease in the relative risk of disease relapse or death observed with dabrafenib plus trametinib vs placebo (HR=0.47 [95% CI, 0.39-0.58]; P<0.001; median RFS, not reached in the dabrafenib+trametinib arm vs. 16.6 months in the placebo arm, respectively). RFS benefit with the combination treatment was observed across all patient subgroups analyzed, including BRAF mutation status, sex, age, disease stage, the presence of micro- or macrometastases and/or ulceration, and the number of nodal metastases. The OS results at the first interim analysis showed a favorable trend towards survival benefit in the dabrafenib + trametinib arm. Although the OS data was not mature, results favored the dabrafenib + trametinib arm, (HR, 0.57 [95% CI, 0.42-0.79]; P=0.0006); despite this low P value, the interim statistical significance threshold of $P=1.9 \times 10^{-5}$ was not reached. The combination treatment also resulted in DMFS and FFR improvements (49% and 53%, respectively) consistent with the RFS improvement observed (Long, 2017). In addition, the safety profile of the dabrafenib + trametinib combination in the COMBI-AD study was comparable to that observed in other approved indications, including unresectable/metastatic melanoma where it has been well characterized with consistent results

across two randomized Phase III studies. The AEs were manageable, and no new safety risks were identified.

In unresectable or metastatic melanoma, pyrexia is the most frequently observed adverse event with dabrafenib and trametinib therapy (63% in the COMBI-AD study and 54% in the COMBI-D [MEK115306] and COMBI-V [MEK116513] pooled metastatic melanoma data); the majority of the pyrexia events were of grade 1-2, with the same proportion of grade 3/4 (5%) in both settings. Pyrexia led to hospitalization in 11% of the patients in the adjuvant setting, and a similar proportion of hospitalization is observed in the metastatic setting (12% and 11% in the COMBI-D and COMBI-V, respectively). Pyrexia led to permanent treatment discontinuation in 9% of patients in the adjuvant setting while a lower proportion is observed in the metastatic setting (2% and 3% in the COMBI-D and COMBI-V, respectively). In the adjuvant COMBI-AD study, 87 of 435 patients (20%) in treatment arm experienced at least one of the following adverse outcomes of pyrexia (Grade 3/4 pyrexia, hospitalization due to pyrexia and permanent treatment discontinuation due to pyrexia).

The primary objective of this study is to assess whether an adapted AE-management algorithm for pyrexia will reduce the incidence of grade 3/4 pyrexia, hospitalization due to pyrexia, or permanent treatment discontinuation due to pyrexia compared to historical control from COMBI-AD study.

Introduction to study treatments

Dabrafenib (Tafinlar[®]) is an orally bioavailable, potent and selective RAF kinase inhibitor of human wild-type (WT) BRAF and CRAF enzymes as well as the mutant forms of the BRAF enzyme: BRAF V600E, V600K, and V600D. The mechanism of action of dabrafenib is consistent with competitive inhibition of ATP binding.

Dabrafenib was first approved by the FDA in 2013 as a single-agent oral treatment for unresectable or metastatic melanoma in adult patients with the BRAF V600E mutation. Dabrafenib is currently also approved in the EU, Switzerland, Canada, Australia and multiple other countries for the treatment of adult patients with unresectable or metastatic melanoma with a BRAF V600 mutation. Prior to initiation of dabrafenib, patients must have confirmation of tumor BRAF V600 mutation. These approvals include the following limitation of use: dabrafenib is not indicated for the treatment of wild-type BRAF melanoma. The recommended dose of dabrafenib is 150 mg (two 75 mg capsules) twice daily (BID) (corresponding to a total daily dose of 300 mg).

Trametinib (Mekinist[®]) is a reversible and highly selective allosteric inhibitor of MEK1 and MEK2. MEK proteins are critical components of the MAPK pathway which is commonly hyperactivated in tumor cells. Oncogenic mutations in both BRAF and RAS signals through MEK1 or MEK2 proteins. Trametinib was first approved by the FDA in 2013 as a single-agent oral treatment for unresectable or metastatic melanoma in adult patients with BRAF V600 mutations. Trametinib is currently also approved in the EU, Canada, and Australia and multiple other countries for the treatment of adult patients with unresectable or metastatic melanoma. The recommended dose of trametinib is 2 mg once daily (QD).

Dabrafenib in combination with trametinib was first approved by the FDA in 2014 to treat unresectable or metastatic melanoma in adult patients with BRAF V600 mutations. Dabrafenib and trametinib are currently approved in more than 60 countries worldwide as monotherapies and in combination for the treatment of patients with unresectable or metastatic melanoma with a BRAF V600E/K mutation. More recently, the combination was approved in the EU, the US,

and Switzerland for the treatment advanced non-small cell lung cancer with a BRAF V600 mutation, and applications for this indication are currently under review in other countries.

Based on the positive results of the COMBI-AD study, applications for the adjuvant treatment of patients with Stage III melanoma with a BRAF V600 mutation, following complete resection, are also being submitted worldwide, and are already under review by a number of health authorities.

Please refer to the local product information for details on the exact indications approved in a given country.

